2.3.2. Benefit Assessment

There will be no direct benefit to the healthy participants in this study. However, participants will undergo a medical evaluation during screening (including physical examination, electrocardiogram (ECG), vital signs and laboratory assessments), which may provide important health information. The information obtained in this study will inform the conduct of future clinical studies to contribute to the process of developing new therapies for diseases such as Osteoarthritis where there is high unmet medical need.

2.3.3. Overall Benefit: Risk Conclusion

The safety of each individual participant has been prioritised and the eligibility, monitoring, enhanced monitoring and study level stopping criteria described in Section 7 have been designed to minimise risks to participants associated with exposure to GSK3858279. However, participants will undergo a medical evaluation during screening (including physical examination, electrocardiogram (ECG), vital signs and laboratory assessments), which may provide important health information. Taking into account these measures designed to minimise risks, the potential risks identified in association with GSK3858279 are justified.

3. OBJECTIVES AND ENDPOINTS

Objectives	Endpoints
Primary	

 To evaluate the safety and tolerability of a single SC dose of GSK3858279 compared with placebo administered to healthy participants including cohorts of Japanese, Chinese and Caucasians 	
 Incidence of adverse events (AEs), serious adverse events (SAEs), withdrawals due to AEs Occurrence of clinically important changes from baseline in clinical laboratory parameters (haematology, clinical chemistry, urinalysis), vital signs (blood pressure, heart rate, body temperature), and cardiac parameters (electrocardiogram)

 To assess the pharmacokinetic (serum PK) profile up to 56 days following a single SC dose of GSK3858279 in healthy participants including cohorts of Japanese, Chinese and Caucasians 	
 PK parameters: area under the concentration-time curve (AUC(0-56), AUC(0-t) post-dose), time of occurrence of last quantifiable concentration (tlast), maximum observed concentration (Cmax), and time of occurrence of Cmax (tmax) per cohort as data permits
Secondary	

 To evaluate target engagement (TE) up to 56 days following a single SC dose of GSK3858279 in healthy participants including cohorts of Japanese, Chinese and Caucasians. 	
 Reduction (%) from baseline in free CCL17: maximum, minimum and at Days 7, 14, 28 and 56, post-dose Total CCL17 (free and when bound to GSK3858279): maximum observed concentration (Cmax), time of Cmax (tmax), maximum fold increase compared to baseline, fold increase compared to baseline at Days 7, 14, 28 and 56, post-dose.

 To assess the potential for anti-drug antibody (ADA) formation 	
 Incidence of pre-existing ADAs Incidence of treatment-emergent ADAs over time (and whether neutralising)
Exploratory	
CCI	

Objectives	Endpoints
CCI	

4. STUDY DESIGN

[figure not shown]
4.1. Overall Design

This is a randomised, double-blind, placebo-controlled, multi-centre study with a single SC dose of GSK3858279 administered to healthy Caucasian, Chinese and Japanese participants.

[figure not shown]
- Participants will attend a screening visit at the clinical units within 28 days of Study Day 1. If eligible for the study, participants will return on Day -1 and will be admitted to the unit overnight for final screening checks in preparation for randomization and dosing (Day 1).
- Participants will be randomized to either GSK3858279 or placebo in a ratio of 7:3 per cohort.
- Each participant will receive a **CCI** SC dose of GSK3858279 or placebo, administered as four separate SC injections.
- Participants will then remain as an inpatient until discharged on Day 3 after assessments have been performed.
- Participants will then return to the clinical unit for outpatient visits as described in the SoA.
 - It will be mandatory for the Caucasian cohort to continue **CCI**, where they will have their final follow up visit at the clinical unit. The final required follow up visit will be at the clinical unit on **CCI** for Chinese and Japanese participants. NB: Japanese and Chinese participants have an option to remain in the study until **CCI**
 - The maximum dose will not exceed **CCI** SC

4.2. Scientific Rationale for Study Design

CCI

CCI

CCI

4.4. End of Study Definition

The end of the study is defined as the date of the last visit of the last participant in the study.

A participant is considered to have completed the primary endpoint if he or she has completed the treatment and day 57.

A participant is considered to have completed the study if he or she has completed the treatment and follow-up phases of the study including the last scheduled procedure shown in the SoA.

5. STUDY POPULATION

Prospective approval of protocol deviations to recruitment and enrolment criteria, also known as protocol waivers or exemptions, is not permitted.

5.1. Inclusion Criteria

Participants are eligible to be included in the study only if all of the following criteria apply:

TYPE OF PARTICIPANT AND DISEASE CHARACTERISTICS	
1. Participants who are overtly healthy as determined by medical evaluation including medical history, physical examination, laboratory tests and cardiac monitoring [12-lead ECGs].	A participant with a clinical abnormality or laboratory parameter(s) outside of the reference range for the population being studied that is not specifically listed in the inclusion or exclusion criteria may be included if the Investigator (in consultation with the GSK Medical Monitor if required) agrees and documents that the finding is unlikely to introduce additional risk factors and will not interfere with the study procedures or interpretation.
AGE	
2. Between 20 and 65 years of age inclusive, at the time of signing the informed consent.	
INFORMED CONSENT	
3. Capable of giving signed informed consent which includes compliance with the requirements and restrictions listed in the informed consent form (ICF) and in this protocol.	
COVID-19 (SARS CoV-2) Vaccination	
4. Participants who have evidence of completed vaccination for SARS-CoV-2 with an approved vaccine	
WEIGHT	
5. Body weight within the range 45 – 100 kg and body mass index (BMI) within the range 18-29.9 kg/m ² (inclusive) for Chinese and Japanese participants. Caucasian participants must exhibit BMI range of 18 – 32.0 kg/m ² .	
GEOGRAPHICAL ANCESTRY	
6. Japanese Participants are eligible based on meeting all of the following:	

 • Participants born in Japan • Descendants of four ethnic Japanese grandparents and two ethnic Japanese parents • Have lived outside Japan for less than 10 years at the time of screening 	
7. Chinese Participants are eligible based on meeting all of the following:	

- Participant born in mainland China, Hong Kong or Taiwan
- Descendants of four ethnic Chinese grandparents and two ethnic Chinese parents
- Have lived outside mainland China, Hong Kong or Taiwan for less than 10 years at the time of screening
- 8. Caucasian Participants are eligible based on meeting the following:
- Declaration of familial Caucasian/European ancestry (having 2 parents of Caucasian/European ancestry and 4 grandparents of Caucasian/European ancestry)

SEX**9. Male or female participant:****a. Male participants:**

Male participants are eligible to participate if they agree to the following for at least 28 weeks after the dose of study intervention:

- Refrain from donating sperm

PLUS either:

- Be abstinent from heterosexual intercourse as their preferred and usual lifestyle (abstinent on a long term and persistent basis) and agree to remain abstinent

OR

- Must agree to use contraception/barrier as detailed below

- Agree to use a male condom
- and should also be advised of the benefit for a female partner to use a highly effective method of contraception (see Section 10.4) as a condom may break or leak when having sexual intercourse with a woman of childbearing potential who is not currently pregnant

b. Female participants:

A female participant is eligible to participate if she is of non-reproductive potential as defined in Section 10.4.

5.2. Exclusion Criteria

Participants are excluded from the study if any of the following criteria apply:

MEDICAL CONDITIONS

1. History or presence of cardiovascular, respiratory, hepatic, renal, gastrointestinal, endocrine, haematological, or neurological disorders capable of significantly altering the absorption, metabolism, or elimination of drugs; constituting a risk when taking the study intervention; or interfering with the interpretation of data.
 
2. Personal or family history of cardiomyopathy.
 
3. Abnormal blood pressure at screening as determined by the investigator.
 
4. History of symptomatic herpes zoster
 
5. Evidence of active or latent tuberculosis (TB) as documented by medical history, examination, and TB testing with a positive (not indeterminate) QuantiFERON test.
 
NOTE: In cases where the QuantiFERON test is indeterminate, the participant may have the test repeated once, but they will not be eligible for the study unless the second test is negative. In cases where the QuantiFERON test is positive, the participant should be followed up as per standard of care. If a locally-read follow up chest x-ray shows no evidence of current or previous pulmonary tuberculosis, the participant may be eligible for the study at the discretion of the Investigator and GSK Medical Monitor.
 
6. Significant allergies to humanized monoclonal antibodies as per principal investigator's and GSK medical monitor's judgements.
 
7. History or evidence of clinically significant multiple or severe drug allergies, intolerance to topical corticosteroids, or severe post-treatment hypersensitivity reactions (including, but not limited to, erythema multiforme major, linear immunoglobulin A (IgA) dermatosis, toxic epidermal necrolysis, and exfoliative dermatitis)
 
8. History of lymphoma, leukaemia, or any malignancy within the last 5 years except for basal cell or squamous epithelial carcinomas of the skin that have been resected with no evidence of metastatic disease for 3 years.
 
9. Alanine transaminase (ALT) $>1.5 \times$ upper limit of normal (ULN)
 
10. Bilirubin $>1.5 \times$ULN (isolated bilirubin $>1.5 \times$ULN is acceptable if bilirubin is fractionated and direct bilirubin $<35\%$).
 
11. Current or chronic history of liver disease, or known hepatic or biliary abnormalities (with the exception of Gilbert's syndrome or asymptomatic gallstones)
 
12. Corrected QT (QTc) >450 msec
 
NOTES:


- The QTc is the QT interval corrected for heart rate according to Bazett's formula (QTcB), Fridericia's formula (QTcF), and/or another method, machine-read or manually over-read.
- The specific formula that will be used to determine eligibility and discontinuation for an individual participant should be determined prior to initiation of the study. In other words, several different formulae cannot be used to calculate the QTc for an individual participant and then the lowest QTc value used to include or discontinue the participant from the trial.
- For purposes of data analysis, QTcF, another QT correction formula, or a composite of available values of QTc will be used as specified in the Reporting and Analysis Plan (RAP).

13. History of Stevens Johnson Syndrome
14. Known immunodeficiency
15. Participants with a chronic infection (e.g., osteomyelitis), who have been receiving treatment within three months prior to dosing or individuals with an active infection.
16. Previous or current history of bleeding diathesis, excessive bleeding or coagulation disorders
17. History of significant medical illness in the opinion of the investigator would interfere with the study procedures and / or assessments

PRIOR/CONCOMITANT THERAPY

18. Intended use of over-the-counter or prescription medication including herbal medications within 7 days prior to dosing (or 14 days if the drug is a potential enzyme inducer) or 5 half-lives (whichever is longer) before the start of study intervention until completion of the follow-up visit, unless, in the opinion of the investigator and sponsor, the medication will not interfere with the study.
19. Live vaccine(s) or plans to receive such vaccines within 1 month of screening until final follow-up visit.
20. Treatment with biologic agents (such as monoclonal antibodies including marketed drugs) within 3 months or 5 half-lives (whichever is longer) prior to dosing
21. Treatment with antiplatelet or anticoagulant agents within 7 days of dosing
22. Major surgery (as per investigator's judgement) within 3 months prior to dosing

PRIOR/CONCURRENT CLINICAL STUDY EXPERIENCE

23. Participation in the study would result in loss of blood or blood products in excess of 500 mL within 3 months.


24. Exposure to more than 4 new chemical entities within 12 months prior to the first dosing day.
 
25. Current enrolment or past participation in any other clinical study involving an investigational drug intervention within the last 3 months or 5 half-lives (whichever is longer) of signing the ICF

--

DIAGNOSTIC ASSESSMENTS

26. Presence of Hepatitis B surface antigen (HBsAg) at screening.
 
27. Presence of the Hepatitis B core antibody (HBcAb) at screening.
 
28. Positive Hepatitis C antibody test result at screening.
 
NOTE: Participants with positive Hepatitis C antibody due to prior resolved disease can be enrolled, only if a confirmatory negative Hepatitis C RNA test is obtained
 
29. Positive Hepatitis C RNA test result at screening or within 3 months prior to first dose of study intervention
 
NOTE: Test is optional and participants with negative Hepatitis C antibody test are not required to also undergo Hepatitis C RNA testing.
 
30. Abnormal clinically significant echocardiogram at screening, as assessed by the investigator.
 
31. Cardiac troponin or NT-proBNP levels out of normal range at screening.
 
32. Positive pre-study drug/alcohol screen
 
33. Positive human immunodeficiency virus (HIV) antibody test
 
34. Positive coronavirus (COVID-19): SARS-CoV2 PCR or lateral flow test of a combined throat and nasopharyngeal swab or nasal swab only

OTHER EXCLUSIONS

35. Regular alcohol consumption within 6 months prior to the study defined as:
 
 • an average weekly intake of >11 standard drinks for males and females. One standard drink contains 10g of alcohol. 
36. Regular use of known drugs of abuse.
 
37. Sensitivity to any of the study interventions, or components thereof, or drug or other allergy that, in the opinion of the investigator or medical monitor, contraindicates participation in the study.

--

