1.3. Schedule of Activities (SoA)

Screening period

Procedure	Screening (Day -28 to Day -1)
Informed consent	X
Inclusion and exclusion criteria	X
Demography	X
Full Physical examination including height and weight	X
Medical/medication/drug/alcohol history ¹	X
Alcohol & Tobacco screens ²	X
Urine drug screen	X
FSH (in WONCBP)	X
HIV, Hepatitis B and C screening	X
Haematology, clinical chemistry, urinalysis	X
COVID-19 (SARS-CoV-2) PCR or rapid antigen test	X
TB screening (QuantiFERON)	X
12-lead ECG ³	X
Vital signs ⁴	X
Echocardiogram	X
AE assessment	X
SAE assessment	X
Target Engagement Sample Collection	X

1. To include substance usage, family history of premature cardiovascular disease, medication, drug/alcohol history
2. As per local standard practice
3. Performed in triplicate
4. Vital signs are to be taken before blood collection for laboratory tests

Treatment and Follow-up

Procedure	Treatment and Follow-up (FU)																	
	1	2	3	4	CCI	EW ¹												
Week																		
Day	-2	-1	1 ^a	2 ^a	3 ^a	5 ^b	8 ^b	15 ^b	22 ^b	29 ^b								
Outpatient visit	X					X	X	X	X	X	X	X	X	X	X	X	X	X
Inpatient Stay		X	X	X														
Discharge from clinical unit					X													
Inclusion and exclusion criteria			X ²															
Brief Physical examination			X ³	X				X									X	X
Alcohol & Tobacco screens		X																
Urine drug screen		X																
12-lead ECG (triplicate)		X	X ⁴	X	X		X	X	X	X	X	X	X	X	X	X	X	X
Vital signs		X	X ⁵	X	X		X	X	X	X	X	X	X	X	X	X	X	X
Smoking Status		X				X	X	X	X	X	X	X	X	X	X	X	X	X

Procedure	Treatment and Follow-up (FU)															
	Week						1	2	3	4	CCI	EW ¹				
Day	-2	-1	1 ^a	2 ^a	3 ^a	5 ^b	8 ^b	15 ^b	22 ^b	29 ^b						
Haematology, clinical chemistry, urinalysis		X	X	X	X		X	X	X	X	X	X ⁶	X	X	X	X
COVID-19 SARS- CoV-2 PCR or rapid antigen test	X ⁷															
Randomization			X													
Dosing (SC) injections			X ⁸													
PK & TE	X ⁹		X ¹⁰	X ¹⁰	X ¹⁰	X	X	X	X	X	X	X	X	X	X	X
Immunogenicity			X ¹¹					X		X		X		X		X
PD serum/plasma samples (For protein biomarkers)			X		X		X	X	X	X						X
PD WB PAXgene samples (For transcriptomic analyses)			X		X		X		X							X

Procedure	Treatment and Follow-up (FU)										
	1	2	3	4	CC1	EW ¹					
Week											
Day	-2	-1	1 ^a	2 ^a	3 ^a	5 ^b	8 ^b	15 ^b	22 ^b	29 ^b	
PGx			X ¹²								
SAE and AE (SAEs recorded throughout. AEs recorded from first SC injection)	<----->										X
Concomitant meds	<----->										X

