Risk of Infection	
The intended pharmacologic effect of GSK3858279 may result in an CCI [REDACTED] [REDACTED]. CCI [REDACTED]
	
Participant Selection Participants with active or chronic infections or a history of recent or recurrent infections will not be included in the study – see Section 5.1.
 
Participant Monitoring Participants will be monitored for infection. Participants will be instructed in the ICF as to the signs and symptoms of infection, and to contact the site personnel should they develop.

Potential Risk of Clinical Significance	Summary of Data/Rationale for Risk	Mitigation Strategy
	CCI	
Vaccination Reactions		
Participant selection and non-permitted medications:
 
Attenuated live vaccines should not be administered to participants within 30 days prior to dosing and for five half-lives after dosing. If indicated, non-live vaccines (e.g. inactivated influenza vaccines) may be administered whilst receiving GSK3858279 based on an assessment of the benefit:risk (e.g. risk of decreased responsiveness).

Cardiac Risks		
Participant Exclusion: Participants with a history of cardiac disease or cardiac abnormalities (including abnormal Troponin I and NT-proBNP) that, in the opinion of the investigator, would compromise cardiac safety will be excluded from the study.
 
Participant monitoring: Investigations during screening include ECG,

Potential Risk of Clinical Significance	Summary of Data/Rationale for Risk	Mitigation Strategy
	CCI	echocardiogram and troponin I and NT-proBNP. Troponin I and NT-proBNP will be monitored after dosing.
Bleeding Risk	CCI	Participant exclusion and non-permitted medication Participants with a previous or current history of bleeding diathesis will be excluded.

Potential Risk of Clinical Significance	Summary of Data/Rationale for Risk	Mitigation Strategy
	CC1	Use of anti-coagulants or anti-platelet agents will be prohibited.
Skin Reactions		Participant Exclusion Participants with a history of drug-induced skin reactions and Stevens-Johnson Syndrome will be excluded. Participant Monitoring Clinically significant skin reactions will be reviewed by a dermatologist and, if appropriate, a skin biopsy will be requested for histological analysis.

Potential Risk of Clinical Significance	Summary of Data/Rationale for Risk	Mitigation Strategy

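### Exclusion criterion 5 names latent TB, but its NOTE can admit a QuantiFERON-positive volunteer on a clear chest film, which does not address latent infection

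*Protocol*

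**What the plan says.** Criterion 5 in Protocol Section 5.2 excludes the following: "Evidence of active or latent tuberculosis (TB) as documented by medical history, examination, and TB testing with a positive (not indeterminate) QuantiFERON test". A NOTE under it deals with two test results.

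- **Indeterminate.** The rule is strict: "the participant may have the test repeated once, but they will not be eligible for the study unless the second test is negative".
- **Positive.** The volunteer is to receive standard-of-care follow-up. The NOTE then adds: "If a locally-read follow up chest x-ray shows no evidence of current or previous pulmonary tuberculosis, the participant may be eligible for the study". The decision is joint, since the volunteer "may be eligible for the study at the discretion of the Investigator and GSK Medical Monitor".

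Section 2.3.1 lists infection as a potential risk of clinical significance and describes participant selection in general terms: "Participants with active or chronic infections or a history of recent or recurrent infections will not be included in the study". The product-specific rationale for that risk is redacted.

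**The concern.** The criterion names latent infection as a reason to exclude. The exception lifts the exclusion on a finding that concerns pulmonary disease. A volunteer with untreated latent infection is just the person who could have a positive QuantiFERON and a clear film, so the exception can let in what the criterion is meant to keep out.

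The stake is participant safety. Section 2.3.2 states: "There will be no direct benefit to the healthy participants in this study". Infection is a listed risk of the product, and the product is given once, so nothing remains to be withheld if a problem appears later. The safety, pharmacokinetic and target-engagement analyses do not depend on this sentence.

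**Working it through.** The plan states no figure here to reproduce. The check traces each test result through the text, looks for a safeguard elsewhere, and sizes the cost of a change.

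**1. Each QuantiFERON outcome under criterion 5 and its NOTE**

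| Result | Outcome as written |
|---|---|
| Negative | Not excluded by the test |
| Indeterminate, then negative | Not excluded by the test |
| Indeterminate twice | Excluded, no discretion |
| Indeterminate, then positive | Excluded by the repeat-test sentence |
| Positive | Meets the test element of the exclusion, yet may enter with a clear film and joint agreement |

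The order is inverted: two uninformative results exclude without appeal, while a positive result has a way in.

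**2. What the positive route requires.** There is one objective condition, a locally read film without signs of present or past pulmonary TB. There is one procedural condition, agreement by two parties. Neither asks whether latent infection has been ruled out or treated.

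**3. Whether another provision closes the gap**

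- Criterion 15 covers: "Participants with a chronic infection (e.g., osteomyelitis), who have been receiving treatment within three months prior to dosing or individuals with an active infection". An untreated latent infection is neither recently treated nor active, so it falls outside.
- Criterion 14 (immunodeficiency), criterion 17 (significant medical illness) and inclusion criterion 1 (overt health) do not mention latent TB.
- The selection statement in Section 2.3.1 refers to chronic infection but does not say whether that includes latent TB, and it sets no TB condition.
- Section 5 forbids waivers. Use of the NOTE is not a waiver, because the discretion is written into the criterion.
- The Schedule of Activities has one TB row, the QuantiFERON at screening, and no TB check after dosing.

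**4. How the same section treats another infection.** A positive hepatitis C antibody (criterion 28) can also be overcome, but only by a negative RNA test, which is aimed at the infection named. Hepatitis B core antibody (criterion 27) and HIV antibody (criterion 33) exclude with no such route. The TB exception is the one whose follow-up finding does not match the named condition.

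**5. Expected cost of closing the route.** Let p be the share of otherwise eligible volunteers who are QuantiFERON-positive with a clear film. The documents do not give p, so the values below are assumptions. The number of places per cohort is 10 (Protocol Section 9.3). If all such volunteers are excluded, the expected number of extra otherwise eligible volunteers screened is

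10/(1-p) - 10 = 10p/(1-p)

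- p = 1%: 0.10/0.99 = 0.10
- p = 5%: 0.50/0.95 = 0.53
- p = 10%: 1.00/0.90 = 1.11
- p = 20%: 2.00/0.80 = 2.50

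These are expected numbers. At p = 20% the count is negative binomial with standard deviation sqrt(10 × 0.2)/0.8 = 1.8, so a given cohort could need noticeably more than 2.5. Replacements for participants who withdraw before Day 57 would add places and raise the figure in proportion. In the other direction, joint discretion would already turn some of these volunteers away under the current text.

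**The case against.** The strongest reply is that this is a considered design choice. The NOTE is part of criterion 5, it says how a positive test is to be handled, and entry is allowed but never required. Two parties must agree, and standard-of-care follow-up comes first. The criterion also lists history, examination and testing together, so a positive assay alone may not establish the exclusion, and clinical judgement keeps its place. All of this is fair, and it limits the practical risk. It does not supply a condition on latent infection: the NOTE gives the deciders a film for pulmonary disease and nothing directed at the other half of the criterion. The NOTE also does not say that a positive test alone falls outside the criterion.

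Three stronger readings are tempting, and the documents do not support them.

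- A reader might infer that the criterion contradicts itself through a drafting slip. The exception is explicit and appears deliberate. The fault is that its condition does not match the named infection.
- A reader might infer that indeterminate-then-positive is truly undecided, because the sentences on a positive test are not limited to a first test. The repeat-test sentence is mandatory and specific to that sequence, so it governs over a general permission. Only a clarification is called for.
- A reader might take the absence of a chest x-ray row in the Schedule of Activities as a further defect. The film is a conditional follow-up. The conditional hepatitis C RNA test has no row of its own either, so the absence shows little.

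**Conclusion.** The point holds as a mismatch between criterion 5 and the exception in its own NOTE: a volunteer with the latent infection named as exclusionary can be enrolled on a finding that does not bear on it. Importance is low to moderate.

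The documents give no prevalence, so the number of volunteers who might enter this way cannot be stated. The product-specific infection risk is redacted, so the added risk to such a volunteer cannot be sized either. It would go too far to conclude that the study is unsafe or that such volunteers will be enrolled. Entry is optional and jointly decided. The conclusion rests on the wording alone and on the ordinary understanding that a clear chest film does not exclude latent infection. A change is recommended because it is cheap and because these participants have nothing to gain from carrying the risk.

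**What to change.** **Preferred.** Delete the last sentence of the NOTE and state that a positive QuantiFERON excludes. Keep the sentence on standard-of-care follow-up.

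**Alternative, if the sponsor wants a route.** Limit it to volunteers with documented completed treatment for latent TB and a clear chest x-ray. If latent TB is to count as a chronic infection under criterion 15, that treatment must also have ended more than three months before dosing, and the text should say so.

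**Clarification in the same edit.** Confirm that an indeterminate result followed by a positive one is not eligible, as the repeat-test sentence already implies.

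**Cost.** The preferred change is one sentence deleted and one clause added at the next amendment, with no new test or visit. The downside is the extra screening worked out above. It may fall unevenly across the three cohorts if p differs between them. That matters for recruitment, since the summary of changes shows that the ancestry criterion for the Chinese cohort was widened to help fill it.
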